1.8 Rationale for trial

Changed “uveitic macular edema persistent after intravitreal *triamcinolone* injection” to “uveitic macular edema persisting after an intravitreal *corticosteroid* injection”

2.2 Hypotheses

Changed “uveitic macular edema persistent after intravitreal *triamcinolone* injection” to “uveitic macular edema persisting after an intravitreal *corticosteroid* injection”

3.3 Trial schema

Added intravitreal methotrexate at week 4 (M02) as needed; previously additional injection only was permitted at week 8 (M03) as needed (per recommendation of DSMC)

3.6 Eligibility

Inclusion criterion #3 (eye level) was revised to allow macular edema persisting after intravitreal corticosteroid injection (which includes intravitreal dexamethasone) rather than limiting to macular edema persisting after intravitreal triamcinolone as follows: Macular edema (ME) defined as the presence of macular thickness greater than the normal range for the OCT machine being used, regardless of the presence of cysts, following an intravitreal corticosteroid injection (≥ 28 days following intravitreal triamcinolone injection and ≥ 90 days following intravitreal dexamethasone implant injection)

Inclusion criterion #6 (eye level): At request of DSMC, italicized text was added to clarify that eye being treated with combination therapy is equivalent to use of two IOP-lowering medications as follows: Baseline intraocular pressure > 5 mm Hg and ≤ 21 mm Hg (current use ≤ 2 intraocular pressure-lowering medications and/or prior glaucoma surgery are acceptable — *note that an eye being treated with a combination therapy like Combigan is counted as being*

treated with two IOP-lowering medications, which means, for example, that an eye treated with Combigan and a prostaglandin analogue is not eligible for the trial;

Exclusion criterion #9 (eye level): As recommended by the DSMC, changed “uncontrolled” to “severe” glaucoma as follows: History of severe glaucoma as defined by optic nerve damage (cup/disc ratio of ≥ 0.9 or any notching of optic nerve to the rim);

4.1.1 Schedule of assigned treatment and 4.1.2 Additional injections

For intravitreal methotrexate added that additional injections are permitted as needed at weeks 4 and 8; previously additional injection as needed at week 8 only

4.2.3 Intravitreal methotrexate injection preparation and administration

Removed information and reference describing the use of frozen methotrexate preparations as requested by CC’s IRB as reference from 1988 is out of date.

4.2.4 Intravitreal ranibizumab formulation, storage, and administration

Added: Preparation of injection as requested by CC’s IRB

- Using aseptic technique, remove contents from the vial using a 5 micron, 19 gauge filter needle attached to a 1-cc tuberculin syringe. Remove filter needle and replace with the provided 30 gauge ½ inch needle for injection.

5.1 Safety reporting of adverse events – General overview

This section was revised to reflect timeframe for DSMC Medical Safety Officer’s review of SAE reports as agreed upon at 8 Dec 2015 DSMC meeting. Any SAE reports of a subject death will be sent to DSMC Medical Safety Officer within 24 hours of receipt at the CC. Non-death SAE reports will be sent to the DSMC Medical Safety Officer within 7 days of receipt at the CC. The DSMC Medical Safety Officer will review each report to determine what, if any, additional actions are needed, including whether the other DSMC members need to be informed of the event immediately as opposed to waiting for the next DSMC meeting or conference call.

7.2 IRB/Protection of human subjects

Data and safety monitoring

- Corrected description of new member from “statistician” to “experienced methodologist for ophthalmic studies”
- Clarified that DSMC will meet at least twice a year, one of these meetings being in person and one by conference call and that additional meetings may be arranged at the request of the DSMC Chair and/or the NEI Project Officer.
- Revised timeframe for and clarified that the DSMC Medical Safety Officer will review all SAE reports between meetings as detailed in section 5.1

Typographical errors corrected throughout document

28 Mar 2016, version 1.1

3.3 Trial schema

- Revised retreatment schedule to specify *required* time points for retreatment if retreatment criteria are met and added *permitted* time points for retreatment
- Added minimum time separation between treatments to retreatment criteria

3.6 Eligibility criteria

- Changed “History of infectious uveitis” from eye-level exclusion criterion to patient-level exclusion criterion
- Added eye level exclusion: Torn or ruptured posterior lens capsule

4. Study treatment: section reordered and details added for clarity

- 4.1 Overview section added
- Preparation and administration of study treatment moved to section 5
- 4.2 Treatment schedule by treatment arm
 - 4.2.1 Intravitreal dexamethasone
 - Clarified that retreatment is required at M04 if retreatment criteria met
 - Added retreatment permitted at later time points if retreatment criteria met
 - 4.2.2 Intravitreal methotrexate
 - Clarified that retreatment is required at M02 and M03 if retreatment criteria met; also at M04
 - Added retreatment permitted at later time points if retreatment criteria met
 - 4.2.3 Intravitreal ranibizumab
 - Clarified that retreatment is required at M04 if retreatment criteria met
 - 4.2.4 Retreatment criteria
 - Added minimum time separation between study treatments

5. Study treatment preparation and administration

- Added 5.1 General Requirements to specify who is permitted to administer study treatment and the order of procedures for bilateral injection
- 5.2 added standard pre-injection procedures for all study treatments
- 5.4.2 added details for administration of intravitreal methotrexate
- 5.5.3 added details for administration of intravitreal ranibizumab
- 5.6 added standard post-injection procedures and monitoring for all study treatments

Additionally, typographical errors were corrected throughout document.

2 August 2016, version 1.2

Global changes

- Maximum number of IOP lowering agents for eligibility and retreatment increased from 2 to 3
- Correction of typographical errors and minor text changes for sake of brevity/clarification

3.3 Trial schema

- Retreatment IOP criterion modified by increasing the number of IOP-lowering meds permitted from ≤ 2 to ≤ 3 as in: *≤ 25 mm Hg with ≤ 3 IOP lowering agents permitted*
- Minimum time before retreatment: Added clarifications that while the minimum *target* time between injections is 12 weeks for dexamethasone and 4 weeks for methotrexate and ranibizumab, re-injection is permitted as early as 5 days before these targets, i.e., re-injection is permitted as early as 79 days since previous dexamethasone injection and 23 days since previous methotrexate or ranibizumab injection.

3.6 Eligibility

Inclusion criteria

- 2, 3, 5, &6 - changed “28 days” to “4 weeks” for style consistency
- 3- Changed time following intravitreal dexamethasone from ≥ 90 days to ≥ 12 weeks for consistency with exclusion criterion # 15
- 5 - Removed upper limit of best corrected visual acuity (BCVA) for eye-level eligibility; revised criterion is BCVA better than 5/200
- 6 - Increased the maximum number of IOP lowering medications permitted from 2 to 3 as follows: Baseline intraocular pressure > 5 mm Hg and ≤ 21 mm Hg (current use ≤ 3 intraocular pressure-lowering medications and/or prior glaucoma surgery are acceptable —; note that combination medications, e.g., Combigan count as two IOP-lowering medications);

Exclusion criteria

- 5 & 6 - changed “28 days” to “4 weeks” for style consistency
- 3 - Added new patient-level exclusion: History of serous retinopathy in either eye
- 5 - Clarification added as italicized for exclusion: oral prednisone dose ≤ 10 mg per day *at baseline* that has not been stable for at least 4 weeks (*Note: If patient is off of oral prednisone at baseline (P01 visit), dose stability requirement for past 4 weeks does not apply*)
- 15 & 16 Changed exclusion for anti-VEGF agent and intravitreal methotrexate from administered in *past 12 weeks* to administered in *past 4 weeks*

4.1 [Treatment] overview

- Pregnancy testing required for women of childbearing potential before additional intravitreal injections of methotrexate or ranibizumab

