3.5. Secondary outcomes

- Rates of IOP elevation of ≥ 24 mm Hg, ≥ 30 mm Hg, and ≥ 10 mm Hg from baseline during the 24 weeks of follow-up
- Percent change in macular thickness as measured by OCT over the 24 weeks of follow-up
- Proportion of eyes with macular edema events over the 24 weeks of follow-up
 - $\geq 20\%$ reduction in macular thickness (or normalization of macular thickness even if there is $<20\%$ reduction)
 - "Resolution", defined as normalization of the macular thickness, i.e., <260 μm on the standard scale Worsening defined as a 20% increase in macular thickness from the lowest value after an injection
 - "Recurrence" defined as $>20\%$ increase in the central subfield measurement on OCT to an abnormal value in an eye that previously had resolution of ME
- Mean change in BCVA over the 24 weeks of follow-up.
Best-corrected visual acuity score will be measured at every study visit under standardized lighting conditions by certified study examiners masked to study treatment using logarithmic (ETDRS) visual acuity charts, according to the method described by Ferris, et al.¹²⁷
- Safety outcomes including elevated IOP (>30 mm Hg thresholds); vitreous hemorrhage; retinal tear/detachment; endophthalmitis; severe vision loss (≥ 15 Early Treatment Diabetic Retinopathy Study [ETDRS] letters) during the 24 weeks of follow-up.

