3.6. Eligibility criteria

Inclusion criteria:

Patient level inclusion criterion

1. 18 years of age or older;

Eye level inclusion criteria - at least one eye must meet all of the following conditions

2. Inactive or minimally active non-infectious anterior, intermediate, posterior or panuveitis, as defined by SUN² criteria as $\leq 0.5+$ anterior chamber cells, $\leq 0.5+$ vitreous haze grade and no active retinal/choroidal lesions for a minimum of 4 weeks;
3. Macular edema (ME) defined as the presence of macular thickness greater than the normal range for the OCT machine being used (see cut points below), regardless of the presence of cysts, following most recent intravitreal corticosteroid injection (≥ 4 weeks following intravitreal triamcinolone injection or ≥ 12 weeks following intravitreal dexamethasone implant injection);

*Greater than 300 μm for Zeiss Cirrus
Greater than 320 μm for Heidelberg Spectralis
Greater than 300 μm for Topcon 3DOCT*

4. Best corrected visual acuity (BCVA) 5/200 or better;
5. Baseline intraocular pressure > 5 mm Hg and ≤ 21 mm Hg (current use of ≤ 3 intraocular pressure-lowering medications and/or prior glaucoma surgery are acceptable (*Note: combination medications, e.g., Combigan, are counted as two IOP-lowering medications*));
6. Media clarity and pupillary dilation sufficient to allow OCT testing and assessment of the fundus.

Exclusion criteria:

Patient level exclusion criteria

1. History of infectious uveitis in either eye;
2. History of infectious scleritis of any type in either eye (*Note: History of noninfectious scleritis that has been active in past 12 months is an eye-level exclusion –see #13 below*);
3. History of keratitis (with the exception of keratitis due to dry eye) in either eye;
4. History of central serous retinopathy in either eye;
5. Active infectious conjunctivitis in either eye;
6. Oral prednisone dose > 10 mg per day (or of an alternative corticosteroid at a dose higher than that equipotent to prednisone 10 mg per day) OR oral prednisone dose ≤ 10 mg per day at baseline that has not been stable for at least 4 weeks (*note: if patient is*

off of oral prednisone at baseline (M01 study visit) dose stability requirement for past 4 weeks does not apply);

7. Systemic immunosuppressive drug therapy that has not been stable for at least 4 weeks (*note: use of systemic methotrexate is acceptable as long as regimen has been stable for at least 4 weeks*);

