9.2. Statistical methods

The primary outcome variable is change in log retinal thickness at 12 weeks. A linear regression model fitted with generalized estimating equations¹³² will be used to compare the change in log retinal thickness between each of intravitreal methotrexate and ranibizumab with dexamethasone. The mean structure will include treatment effects, a time indicator for weeks 4, 8, 12, 16, 20, and 24, and time-by-treatment interaction terms. The interaction term for 12 weeks represents the difference in change in log retinal thickness from baseline. An unstructured or Toeplitz covariance matrix will be used to model the longitudinal, within-eye repeated measures and the bootstrap will be used to adjust the standard errors to account for the between-eye correlation. Other continuous and binary outcomes will be modeled in a similar manner using linear and logistic models, respectively. In addition, the models will be adjusted for the stratification variable used during randomization (presence or absence of concomitant systemic corticosteroid and/or immunosuppressive therapy).

Kaplan Meier curves will be plotted to graphically portray the cumulative percent with improvement of ME based on OCT central subfield assessment over time for the three treatments. Cox proportional hazards models taking into account the correlation between eyes

through a random effect (also known as a frailty model) will be used to compare the time to improvement of ME for the three treatment arms. Additional time-to-event outcomes (e.g. time to resolution, failure, and relapse) will be analyzed in a similar manner.

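### The models for IOP of at least 24 and at least 30 mm Hg use no baseline IOP information, although entry IOP and pressure-lowering treatment vary widely; adjusting for them is a cheap, modest gain in power

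*Combined protocol and SAP*

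**What the plan says.** **Entry.** Section 3.6, inclusion criterion 5, sets "Baseline intraocular pressure > 5 mm Hg and ≤ 21 mm Hg" and adds that "current use of ≤ 3 intraocular pressure-lowering medications and/or prior glaucoma surgery are acceptable". The limit of three agents dates from version 1.2, whose entry in the revision history reads "Increased the maximum number of IOP lowering medications permitted from 2 to 3". A combination product counts as two agents. Severe glaucoma is an eye-level exclusion.

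**Outcomes.** The first item in section 3.5 is the rate of IOP elevation on three definitions: at least 24 mm Hg, at least 30 mm Hg, and a rise of at least 10 "mm Hg from baseline during the 24 weeks of follow-up". The first two are absolute levels; only the third refers to the eye's own starting value.

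**Analysis.** Section 9.2 models the primary outcome by GEE with treatment, visit and treatment-by-visit terms. Other continuous and binary outcomes are handled similarly with linear and logistic models. It then states that "the models will be adjusted for the stratification variable used during randomization", and repeats this after the negative binomial model for adverse event rates. That variable is concomitant systemic corticosteroid or immunosuppressive therapy, yes or no, which is also the only stratification factor (sections 3.1 and 3.7). Baseline IOP, number of agents and prior glaucoma surgery are not named as covariates.

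**Data.** Section 3.8 schedules tonometry and treatment history at M01. The agent count must be known for each study eye to establish eligibility.

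**The concern.** Tolerability is half of the objective in section 2.1, and the abstract names less IOP elevation as a potential advantage of the two non-steroid treatments. An IOP comparison between arms will therefore be read closely.

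How far an eye must rise to count as an event depends on where it starts. An eye entering at 8 mm Hg must rise 24 − 8 = 16 mm Hg to reach 24; an eye entering at 21 mm Hg needs 24 − 21 = 3. The planned model treats the two alike within a systemic-therapy stratum. If baseline IOP predicts crossing the threshold, leaving it out wastes information in an analysis for which the documents give no power figure. A chance difference in baseline IOP between arms would also feed into the estimate from the one trial that is run. Adjustment decided on only after such a difference is seen would look selective.

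**Working it through.** **1. The plan's own figure.** Section 9.1 gives power only for retinal thickness. Inputs: 79 independent eyes per arm, reductions of 25% and 38%, SD 0.33, two-sided alpha 0.025.
- Difference: ln(0.75) − ln(0.62) = 0.190. SE: 0.33 × √(2/79) = 0.0525.
- Power: Φ(0.190/0.0525 − 2.241) = 91.7% (91.2% with the t distribution), against 91% stated.
- Effective eyes: 80 × 0.9 × (0.75 + 0.25 × 2/1.4) = 79.7, against 79.

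These figures reproduce. No corresponding figure exists for IOP, so everything on power below rests on assumed inputs.

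**2. What baseline contributes to each outcome.** Entry IOP is capped at 21 mm Hg, so the indicators for at least 24 and at least 30 are zero at M01 for every eligible eye. A model built on change from baseline learns nothing from them about differences between eyes. For the rise of at least 10 mm Hg, baseline is already in the definition.

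**3. Chance imbalance.** With 80 patients per arm, the between-arm difference in a standardized baseline covariate has SD √(2/80) = 0.158. It exceeds 0.2 SD in either direction with probability 21%, and 0.3 SD with probability 6%.

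**4. Power with and without the covariate.** Assumptions: 79 independent eyes per arm, one event indicator per eye, a logistic model, two-sided 5% test, 3,000 trials per row, and one standardized baseline covariate with the odds ratio (OR) shown. Event rates are assumed.

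| Event rates | OR per SD | Rejection, unadjusted | Rejection, adjusted |
|---|---|---|---|
| 20% v 20% | 1.5 | 4.3% | 4.5% |
| 20% v 20% | 2 | 4.6% | 4.6% |
| 20% v 20% | 3 | 4.4% | 5.0% |
| 20% v 8% | 1.5 | 57.6% | 58.3% |
| 20% v 8% | 2 | 57.1% | 59.9% |
| 20% v 8% | 3 | 57.3% | 64.0% |
| 30% v 15% | 1.5 | 60.4% | 61.3% |
| 30% v 15% | 2 | 61.7% | 65.3% |
| 30% v 15% | 3 | 62.3% | 71.0% |

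The gain is under 1 point for a weak predictor, about 3 to 4 points at OR 2, and about 7 to 9 points at OR 3. With no predictive value (OR 1), type I error was 4.6% either way and power was unchanged within simulation error.

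**5. Where the gain comes from.** For 20% v 8% at OR 3, the mean SE of the log odds ratio rises with adjustment, from 0.530 to 0.575. The mean estimate rises more, from 1.117 to 1.289. The ratio of estimate to SE goes from 1.117/0.530 = 2.11 to 1.289/0.575 = 2.24. The gain is in power, not in a smaller SE on that scale.

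**6. Which thresholds benefit.** A visit-level simulation used 80 per arm, six follow-up readings, mean IOP 14 mm Hg plus 1 per agent, between-eye SD 2.5 to 3.5, visit SD 2 to 2.5, and 20 to 30% steroid responders with a 6 to 8 mm Hg rise, all assumed. Adjusting for baseline IOP and agent count was worth 6 to 17% more effective sample size for at least 24 mm Hg, but 0 to 7% for the rise of at least 10.

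**The case against.** The best case for the plan is that adjusting for the randomization stratum alone is a legitimate prespecified choice. No IOP comparison is powered or called the main safety analysis, and the size of any gain cannot be derived from the documents. All of that stands, and it limits the point to efficiency.

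Three stronger readings are tempting and are not supported.

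- *That version 1.2 opened up the entry range.* It raised only the agent limit for this criterion. The revision history's account of an earlier change already shows "Baseline intraocular pressure > 5 mm Hg and ≤ 21 mm Hg (current use ≤ 2 intraocular pressure-lowering medications" and "and/or prior glaucoma surgery are acceptable". The point belongs to the current sections 3.6, 3.5 and 9.2.
- *That chance imbalance biases the comparison or inflates its error rate.* Randomization protects the unadjusted test on average, as the 20% v 20% rows show. A worse figure appears only in selected trials. Under the assumptions of step 6 with identical arms, 13% of trials had a baseline difference of 0.8 mm Hg or more. Given such a difference, the median odds ratio was 1.33 unadjusted and 0.98 adjusted, with unadjusted rejection of 9.6%. If overall rejection is 4.5 to 5%, the remaining trials reject at (4.5 − 0.13 × 9.6)/0.87 = 3.7% to (5 − 0.13 × 9.6)/0.87 = 4.3%. This describes sensitivity of one realized result, not an invalid test.
- *That adjustment will narrow the interval for the odds ratio.* Step 5 shows its SE increasing.

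What the objection does not answer is that nothing in section 9.2 already supplies baseline IOP to the two absolute thresholds.

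**Conclusion.** The point holds as a minor efficiency improvement. The analyses of IOP of at least 24 and at least 30 mm Hg ignore a baseline measurement that every study eye has. The planned comparison remains valid, with type I error of about 5%. Under the assumed event rates and prognostic strength, adjustment is worth about 0 to 9 points of power: near nil for a weak predictor, and at the upper end only for an odds ratio of 3 per SD. It also makes the realized estimate less sensitive to chance baseline imbalance. The benefit is small for the rise of at least 10 mm Hg. The power figures use one independent eye per patient and no repeated visits, whereas section 9.2 plans longitudinal models, so they show order of magnitude only. The primary analysis is unaffected.

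**What to change.** In section 9.2, prespecify the covariates for the IOP-threshold models, alongside the stratification variable:

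- **At least 24 mm Hg:** baseline IOP (continuous) and number of baseline IOP-lowering agents (0 to 3, counted as in section 3.6).
- **At least 30 mm Hg:** baseline IOP only, because events are likely to be few.
- **Rise of at least 10 mm Hg:** baseline IOP may be included for consistency, with little gain expected.

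Report standardized risk differences by arm, since the adjusted odds ratio does not estimate the same quantity as the unadjusted one. The patient-level bootstrap already allowed in section 9.2 can supply the intervals. Prior glaucoma surgery can be tabulated by arm rather than modelled.

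The cost is analysis wording only, with no new data and no change to eligibility or treatment. The downside is one or two extra parameters where events are few, which is why the set is reduced for 30 mm Hg. The wording should be fixed before IOP results by arm are examined.

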4.2.4 Retreatment criteria

- Minimum time between treatments: reduced by 5 days as follows
 - Intravitreal dexamethasone pellet: retreatment permitted as early as 79 days following last treatment; “minimum target” remains 12 weeks
 - Intravitreal methotrexate: retreatment permitted as early as 23 days; “minimum target” remains 4 weeks
 - Intravitreal ranibizumab: retreatment permitted as early as 23 days; “minimum

target” remains 4 weeks

5.2 Standard pre-injection procedures for all study treatments

- Added general requirements
 - Treatment administrator and assistant wear masks during injection procedure
 - Everyone (including patient) is asked not to talk during procedure (to decrease risk of endophthalmitis)
- In last paragraph “Examples of approaches that may be used in study participants with prior adverse reactions associated with povidone-iodine” removed last sentence suggesting investigator discuss with Protocol Chair if circumstance such that alternative approaches presented for use of povidone-iodine are non-viable.

5.3 Administration of intravitreal dexamethasone pellet; inserted following into bulleted instructions

- Mark injection site ocular surface 3.5-4.0 mm posterior to limbus
- Added instruction to displace the conjunctiva with a cotton top applicator held in non-dominant hand prior to injection

